Data collection: daily PA measures, demographic details, co-morbidity status, physical frailty assessment, functional status, quality of life (QOL) and NEHA data

Consent: for participation in the study, physical frailty assessment, additional collection of retrospective CIED data, and access to electronic patient records

Data sources: CIED downloads, self-report questionnaire, physical measurements (height, weight, hand grip strength, gait speed), electronic hospital records, HES (hospital episode statistics) data

Results analysis: data will be analysed to investigate: daily PA variability; the association between PA and NEHAs, and the impact of frailty on PA patterns

Scientific and medical opportunities

This study will collect a unique set of new data for analysis. Combining expertise in Geriatric Medicine and Cardiology, this work will aim to provide a scientific basis for some of the fundamental assumptions made regarding health behaviours in later life. Little is known about normal day-to-day fluctuations in PA in an older population. This objective data will shed light on these patterns, and the temporal relationship between PA and NEHAs. Not only will this enhance our clinical knowledge, but it will provide the opportunity to develop proactive monitoring systems – potentially using PA as a proxy marker of health in certain older patient groups.

Expected outcomes

This study expects to find that NEHAs are commonly preceded by a demonstrable acute decline in PA. Various models will be tested to demonstrate predictive validity. This association is expected to vary by patient sub-groups defined by baseline health status (co-morbidity burden, degree of frailty), and demonstrated underlying activity pattern.

Further avenues for research

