Stroke/TIA	
 • Self-report • Coded on electronic medical records

	
• Brain imaging demonstrating previous ischaemic or haemorrhagic event
--	--

Withdrawal from Study

All participant derived data will be collected on the day of consent, bar the occasional case where a participant wishes to take the questionnaire home and post in back at a later date. Given the short period of time each participant will be actively enrolled in the study, it is highly unlikely a withdrawal of consent will occur. In the event of withdrawal of consent, a consent withdrawal form will be used to document this event. All data collected up to the date of consent withdrawal will be retained, but no further outstanding data collected. This will be made clear in the study information and consent form.

Statistical Analysis

Basic variables from CIED data

CIED data will be processed to create a new set of basic variables for analysis.

1. Mean daily physical activity (MDPA) – mean PA across dataset
2. PA intra-individual variability – as measured by:
 - Range
 - Interquartile range
 - Mean absolute deviation
3. PA surrounding NEHAs – multiple measures.

DOEDA = date of emergency department attendance; DOA = date of hospital admission; DOD = date of discharge; LOS = length of stay (DOD-DOA)

- Difference in PA from MDPA on DOEDA/DOA day -1, day -2, day-3, day-7, day -14
- Difference in PA from MDPA on DOEDA/DOD day +1, day +2, day+3, day+7, day +14
- ‘Time till PA recovery’ – time from DOEDA/DOD to day regained \geq MDPA

Descriptive analyses

All data will be stored and analysed using SPSS and ‘R’ statistical computing software. Basic descriptive statistics will be used to compare different sub-groups of participant (e.g. frail v non-frail). MDPA will be used to facilitate basic comparative analysis using a continuous variable. Determinants of MDPA will be calculated using univariate and multivariable analysis.

PA patterns

As demonstrated in *Figure 3* below, common activity patterns embedded within CIED PA data will be identified using clustering algorithms. Using these identified subtypes of PA as exposures in a longitudinal model with outcome NEHA, multilevel/hierarchical modelling methods (both classical and Bayesian approaches) will be utilised to investigate associations with outcome.

[figure not shown]

Figure 3

PA and major health events

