For this study, major health events are defined as NEHA episodes. Daily PA in the days leading up to NEHA episodes will be compared to a participant's MDPA, in order to define across the cohort when any observable change in PA is detected by this method. To explore trends in PA preceding NEHA episodes, a nested case control study will be constructed within the dataset, comparing trends in PA preceding NEHA episodes with general trends in PA before index times with no NEHA episodes. This will allow the creation of various 'PA markers' for diagnostic test evaluation methods (sensitivity/specificity, positive and negative predictive value). These PA markers will then be investigated to ascertain if they predict PA subtypes i.e. long-term behaviour patterns. We will also look at how these 'markers' superimposed on identified subtypes can be used to potentially personalise alert systems.

In a similar fashion, we will also explore PA trends following NEHA episodes. There is very little published data on 'recovery time' following hospitalisation episodes in an older population. This study is not powered to investigate this as a primary outcome, however we will measure 'time till PA recovery' following NEHA subtypes (A&E attendance and non-elective hospitalisation episodes), and examine determinants of this.

Risks to Study

Recruitment

A snapshot 'screening' audit using Cardex data in October 2016 found 341 potentially eligible patients on CIED annual follow-up at Manchester Royal Infirmary, an additional 150-250 patients at Wythenshawe are anticipated to be eligible. Recruitment will be undertaken by the PI. An 18-month period has been allocated for initial recruitment. Based on observational studies in similar population, we anticipate a take-up rate of from screening of between 60-80% (56).

Efforts made to maximise recruitment:

- Rigorous screening process
- Recruitment from existing clinical visits
- Low burden of assessment

In the event of lower than anticipated take-up, the recruitment window could be extended beyond 18 months to reach required sample size.

Missing data

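### The longitudinal NEHA model takes only cluster-derived activity subtypes as its PA exposure, with no continuous-PA model beside it and no stated consequence if the clusters merely cut a continuum

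*Combined protocol and SAP*

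**What the plan says.** Under Statistical Analysis, PA patterns, "common activity patterns embedded within CIED PA data will be identified using clustering algorithms". The next sentence goes straight to the outcome model: "Using these identified subtypes of PA as exposures in a longitudinal model with outcome NEHA", fitted by multilevel methods, both classical and Bayesian.

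The subsection on PA and major health events uses the subtypes twice more. On the PA markers: "These PA markers will then be investigated to ascertain if they predict PA subtypes i.e. long-term behaviour patterns". On alerts: "We will also look at how these 'markers' superimposed on identified subtypes can be used to potentially personalise alert systems".

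The plan does define continuous PA variables: mean daily physical activity (MDPA) and three measures of intra-individual variability. Under Descriptive analyses, "MDPA will be used to facilitate basic comparative analysis using a continuous variable", and its determinants are examined. MDPA is also each participant's own reference level around a NEHA. No model is described in which continuous PA level, variability or trend is the exposure and NEHA the outcome.

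The readable text gives no clustering algorithm, input features, rule for the number of groups, stability check, or action if distinct groups are not supported. The figure cited in PA patterns is not shown, so its content cannot be counted as absent.

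**The concern.** Objective 1 is to describe the relationship between PA and NEHAs. In the longitudinal model, that relationship is seen only through cluster labels. Two things follow if PA varies smoothly between people.

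First, the labels are then arbitrary cuts, largely of low against high activity. Many partitioning methods return groups from any data, so such cuts could be reported as behaviour types and carried into proposals for personalised alerts. Nothing in the text prompts the analyst to ask whether the groups are more than that.

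Second, replacing a continuous exposure by group labels discards within-group variation and spends extra degrees of freedom. With about 51 events there is little information to spare.

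**Working it through.** **The plan's own figures.** Expected NEHAs (Sample Size Calculations): 224/659 × 150 = 51.0, as stated. Table 1 reproduces to within 1 in every cell, with two-sided alpha 0.05, ratio 4.4, 17% against 43% or 51%, and no continuity correction: Kelsey 132, 81, 177, 108 and Fleiss 144, 88, 198, 121. That table sizes a binary low/decline exposure, so N = 150 is not itself at fault here.

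**Can clustering return one group?** The documents give no PA mean or SD, so PA distributions are assumed. All data below come from a single population of 150 people with no subtypes.

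| Rule for number of groups | Two or more groups returned |
|---|---|
| k-means, silhouette | always (300/300 in one simulation), by construction: silhouette cannot score one group; mean value 0.57-0.66 |
| Gaussian mixture, BIC, skewed raw-scale PA | 120/120 in one simulation; every skewed cohort in the other |
| Gaussian mixture, BIC, log-scale or normal PA | 0% and 0.5% |
| Gap statistic | 27-48% in one simulation, 0% in the other |

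The answer therefore depends on choices that the plan leaves open.

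**Power cost if risk is log-linear in PA level.** Assume normal PA, 51 events and rate ratio R per SD lower PA. The approximate non-centrality is 51 × (ln R)² × s, where s is the share of PA variance that the exposure keeps. For continuous PA s = 1 with 1 df. For k optimal groups s = 0.64, 0.81, 0.88, 0.92 (k = 2 to 5) with k − 1 df.

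At R = 1.5, (ln 1.5)² = 0.164:
- Continuous: 51 × 0.164 = 8.4, and power is about Φ(√8.4 − 1.96) = Φ(0.94) = 83%.
- Two groups: 8.4 × 0.64 = 5.4, and power is about Φ(√5.4 − 1.96) = Φ(0.36) = 64%.

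Simulation (3,000 cohorts of 150, Poisson counts, likelihood-ratio tests) agrees: 82% continuous, against 64%, 64%, 62-63% and 59% for 2, 3, 4 and 5 groups.

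**Effects implied by the plan.** The ratio 4.4 puts the lowest 1/5.4 = 18.5% of people in the exposed group, so the cut-point is c = −0.896. Under a log-linear risk with slope β per SD, the relative risk of that group against the rest is 4.4 × Φ(c + β)/[1 − Φ(c + β)].
- RR 2.5 gives β = 0.544, or 1.72 per SD (4.4 × 0.362/0.638 = 2.5).
- RR 3 gives β = 0.656, or 1.93 per SD (4.4 × 0.405/0.595 = 3.0).

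| Rate ratio per SD | Continuous | 2-5 groups | Loss (points) |
|---|---|---|---|
| 1.3 | 46% | 29-32% | 14-17 |
| 1.5 | 82% | 59-64% | 17-22 |
| 1.72 (RR 2.5) | 95% | 85-88% | 8-10 |
| 1.93 (RR 3) | 99% | 94-96% | 4-6 |

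A separate simulation with normal PA gave 81% against 61-62% (2-3 groups) at 1.5, and losses of about 4-13 points at the two implied effects. With skewed PA at 1.5, one simulation gave 70% against 46-53% and another 74-79% against 38-47%. At the implied effects the skewed loss was about 9-28 points.

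**The opposite case.** With two genuine types 4 SD apart and RR 2.5, two clusters did slightly better than continuous PA (74% against 71%). At 2 SD apart, continuous PA was still better (49% against 35%).

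**The case against.** A reader might infer that the plan will report subtypes whatever the data show. The documents do not support that. No algorithm is named, methods exist that can return one group, and the figure that might show the workflow is missing. The silhouette result is true by construction and describes one possible choice, not the plan's choice. The gap-statistic results conflict between simulations.

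A reader might also infer that the whole PA-NEHA analysis loses power. It does not. The comparison of daily PA before a NEHA with the participant's own MDPA, and the nested case-control comparison of trends, need no labels. They also lie closest to the low/decline exposure used for sizing.

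Nor does the Summary treat subtypes as established. Under Expected outcomes, "This association is expected to vary by patient sub-groups defined by baseline health status (co-morbidity burden, degree of frailty), and demonstrated underlying activity pattern" states a hypothesis, and the alert wording is tentative.

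Finally, at the plan's own RR of 2.5-3 the loss is modest if PA is normal, and the simulations used mainly PA level, whereas the plan may cluster on shape.

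All of this stands and limits the point. It does not supply a continuous-PA exposure model for NEHA, or a stated consequence when groups are not distinct.

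**Conclusion.** The point holds in a limited form. Subtype labels are the only stated PA exposure in the longitudinal NEHA model and they pass unconditionally into the alert work. The reader of the results would have no continuous model to compare them with and no rule for when the groups deserve to be called types.

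The power figures are conditional. They assume risk that follows PA level, about 51 events, and assumed PA distributions; the Poisson counts in the main calculation carry no extra between-person variation. The loss is largest for moderate effects and skewed PA, smallest at the plan's RR of 3 with normal PA, and can vanish with well-separated types. The concern about interpretation does not depend on those figures. This is a change worth making in an exploratory cohort, not a flaw that undermines the study or its sample size.

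**What to change.** In PA patterns, fit the multilevel NEHA model first with continuous PA features: MDPA and intra-individual variability, which the plan already derives, plus a trend term, on the log scale if PA is skewed. Make subtype labels a secondary exposure, judged by what they add to that model.

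Choose the number of clusters by a method that allows one group and has been checked for skewed data, and report bootstrap stability. Describe the groups as distinct behaviour types, or use them in the alert work under PA and major health events, only if that evidence supports them. Otherwise call them descriptive divisions of a continuum.

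Do not turn this into a p < 0.05 gate, and do not read non-rejection as proof that no subtypes exist. One version of a single-population test (60 runs per setting) detected true groups in 100% of runs at a 2.5 SD shift, but in 48% at 2 SD, 2% at 1.5 SD and 0% at 1 SD.

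The cost is analysis wording and a little more computing, with no new data. The study may have to report that distinct subtypes were not supported.

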By the nature of this study, participants are limited to those with a compatible CIED i.e. have some form of cardiac disease (the majority HF and/or conduction disorders). Cardiovascular disease is a fundamental pillar of ageing, lying on the spectrum of physiological frailty – inherent, and relevant to all older people (43). Therefore, on balance we do believe this population sample is generalisable to an older population with comparable functional status and degree of frailty. This study will be looking at temporal pattern analysis, using this population as a cohort of older people with a common age-associated long-term condition (heart disease). There is no reason to expect this group of patients would behave any differently with regard to PA and major health events compared with any other older patient group. Therefore we believe these results will be of interest out with the cardiac community.

Sample Size Calculations

Using data from previous analyses (21, 22) sample size calculations have been performed based on the Kesley and Fleiss formulas for 'cohort studies', using exposure = low/decline in PA and outcome = NEHA within 6 weeks. We considered a relative risk (RR) of 2.5-3 to be clinically significant in terms of a PA trigger signifying increased risk of NEHA. Sample size estimate thus = **150** participants (using inputs: 95% significance, 80% power, RR 2.5-3, output: 88 – 198, see *Table 1*).

Table 1: Sample size calculations

Variables	Option 1	Option 2	Option 3	Option 4
Two-sided significance level (1-alpha)	95	95	95	95
Power (1-beta, % chance of detecting):	80	80	90	90
Percent of Unexposed with Outcome:	17	17	17	17
Percent of Exposed with Outcome:	43	51	43	51
RR	2.5	3	2.5	3
Ratio of sample size, unexposed/exposed:	4.4	4.4	4.4	4.4
Sample size: Kesley	133	81	177	108
Sample size: Fleiss	145	88	198	121

The SENSE HF study (enrolling adult patients with chronic, stable HF, 6 months follow-up) captured 224 'unscheduled hospital visits' in 132 patients over 659 patient years, i.e. an annual rate of 34%. (44) Using this as a guide, with a sample size of 150 (150 patient years) we would expect to capture approximately 51 NEHA episodes from retrospective data collection.

Study Objectives

1. Describe the relationship between PA and NEHAs in an older CIED cohort
2. Describe daily variability of PA in an older CIED cohort
3. Describe the relationship between PA and NEHAs, and examining whether frailty moderates this relationship

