12. NEHA Episodes (HES)
 - 12.1. A&E attendances
 - 12.1.1. Date
 - 12.1.2. Discharge destination
 - 12.1.3. Main diagnostic codes from attendance
13. Non-elective hospitalisation episodes
 - 13.1.1. Date of admission
 - 13.1.2. Date of discharge
 - 13.1.3. Discharge destination
 - 13.1.4. Main diagnostic codes from admission
 - 13.1.5. Discharge destination

Functional data (self-report questionnaire) (46)

14. Assistance required with activities of daily living (ADLs)

- 14.1. Dressing
- 14.2. Walking across a room
- 14.3. Bathing or showering
- 14.4. Eating
- 14.5. Getting out of bed
- 14.6. Using the toilet

15. Assistance required with instrumental activities of daily living (IADLs)
 - 15.1. Using a map
 - 15.2. Preparing a hot meal
 - 15.3. Shopping for groceries
 - 15.4. Making phone calls
 - 15.5. Taking medications
 - 15.6. Doing work around the house
 - 15.7. Managing money

Medical data

16. Multi-morbidity (hospital records, self-report questionnaire)
 - 16.1. Presence of the long term conditions (LTC) as listed in *Table 3* (54)
17. Presence of multi-morbidity (2+ LTCs)
18. Anti-arrhythmic medication (hospital records)

Cardiac data

19. Most recent left ventricular ejection fraction, systolic and diastolic function (echo parameter) (hospital records)
20. NYHA HF score (I - IV)(55), (self-report questionnaire)
21. AF/pAF/no AF (CIED download)

Device data, (Cardex, CIED download)

22. Type of device
23. Date of insertion

24. Indication for insertion

25. Pacing settings

CIED physiological data, (CIED download)

26. Heart failure risk status (low, medium, high), on day of download

27. OptiVol fluid index, daily

28. Patient activity, daily

29. Average night heart rate, daily

30. Heart rate variability (HRV), daily (note NOT computed if atrial paced >80% of time

31. % Pacing/day, daily

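### Sampling controls for the pre-NEHA comparison saves nothing, because daily PA is already held for all participant-time, and at low control ratios it would cost precision

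*Combined protocol and SAP*

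**What the plan says.** Under Statistical Analysis, PA and major health events, the protocol plans that "a nested case control study will be constructed within the dataset, comparing trends in PA preceding NEHA episodes" with trends before index times at which no NEHA occurred. The same set is to yield PA markers, which are then assessed by sensitivity, specificity and predictive values. No controls-per-case ratio, sampling fraction or matching rule is given.

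The list of CIED physiological data in the Summary of data to be collected includes "Patient activity, daily" for each participant. The Missing data section expects little loss from device downloads.

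Sample Size Calculations works with "exposure = low/decline in PA and outcome = NEHA within 6 weeks", and says that "we would expect to capture approximately 51 NEHA episodes from retrospective data collection".

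**The concern.** A nested case-control design is worth its cost when exposure is expensive to measure on the whole cohort, for example an assay on stored samples. Here the exposure comes with the download, for every stored day of every participant. Sampling event-free times therefore saves no data collection, and it adds the sampling variance of the control set to the variance that the cases already contribute.

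This matters because Objective 4 asks whether a drop in PA precedes NEHA and how well it predicts one, and few events are expected. Two other analyses come close but do not replace this step. The comparison with each participant's own mean daily PA (MDPA) looks at days around NEHAs and has no event-free index times. The longitudinal model under PA patterns takes long-term activity subtypes, not pre-event change, as its exposure.

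**Working it through.** **Inputs, all from Sample Size Calculations and Table 1.** Design values: "95% significance, 80% power, RR 2.5-3". "Percent of Unexposed with Outcome": 17. "Ratio of sample size, unexposed/exposed": 4.4. Event-rate source: 224 visits "in 132 patients over 659 patient years, i.e. an annual rate of 34" per cent. The control ratios m below are assumptions, because the plan gives none.

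**1. The plan's own figures reproduce.**
- Events: 224/659 = 0.340 per patient-year; × 150 = 51.0, as stated.
- Table 1, option 1: p1 = 0.43, p2 = 0.17, r = 4.4, pooled p = (0.43 + 4.4 × 0.17)/5.4 = 0.218. The Fleiss formula without continuity correction gives 26.55 exposed, so 27 + 117 = 144 (stated 145).
- Over the four options, Fleiss gives 144, 88, 198, 121 (stated 145, 88, 198, 121). The other formula gives 132, 81, 177, 108 (stated 133, 81, 177, 108).

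**2. All participant-time.** The exposed share is 1/(1 + 4.4) = 0.185. At RR 2.5 the exposed share among cases is 0.185 × 2.5/(0.185 × 2.5 + 0.815) = 0.362, so 18.5 of 51 cases are exposed and 32.5 are not. Var(log RR) = 1/18.5 + 1/32.5 = 0.085, SE = 0.291.

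**3. Sampled controls.** With m control times per case, add 1/c + 1/d, where c = 51 × m × 0.185 and d = 51 × m × 0.815. For m = 1 this is 1/9.4 + 1/41.6 = 0.130. Power = Φ(ln 2.5/SE − 1.96), with ln 2.5 = 0.916.

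| Control set | Added variance | SE | 95% CI around 2.5 | Power |
|---|---|---|---|---|
| All participant-time | 0 | 0.291 | 1.41 to 4.43 | 88% |
| 1 per case | 0.130 | 0.463 | 1.01 to 6.20 | 51% |
| 4 per case | 0.032 | 0.343 | 1.28 to 4.89 | 76% |
| 10 per case | 0.013 | 0.313 | 1.35 to 4.62 | 83% |
| 20 per case | 0.006 | 0.302 | 1.38 to 4.52 | 86% |

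**4. Sensitivity to method.** The Schoenfeld formula uses the variance under no effect, with efficiency m/(m + 1) for sampling. It gives lower power throughout: 72% with all time, then 44%, 62%, 68% and 70% at 1:1, 1:4, 1:10 and 1:20. Expected information for matched sets, relative to all time, is 37%, 71%, 86% and 93% at those ratios. The variance ratios implied by the table (0.0849/0.2148 = 40% at 1:1 and 0.0849/0.1174 = 72% at 1:4) are close. The absolute power depends on the method, but the relative loss hardly does.

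**5. Clustering.** The 51 are episodes. If the source's pattern holds, they come from 132/659 × 150 = 30 patients. As a rough illustration, multiplying the case variance by 51/30 = 1.7 gives 67% power with all time, 42% at 1:1, 59% at 1:4, 64% at 1:10 and 66% at 1:20.

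**6. Control time available.** 150 × 365 = 54,750 participant-days, so (54,750 − 51)/51 is about 1,070 event-free days per event. This is an upper figure: a device need have been in place only 6 months, and data from the first 12 weeks after implantation are excluded.

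**The case against.** A reader might infer that the plan throws away precision. The documents do not support that. They name a nested case-control comparison but give no ratio, and nothing says that eligible event-free time will be discarded. Every case is kept under either design, and at 20 controls per case the illustrated loss is about 2 points of power. Ratios that high cost nothing here. This stands, and it makes the loss conditional.

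Three further points also stand in part:
- The binary exposure and RR of 2.5 are borrowed from a sizing table with a 6-week outcome. The planned step compares trends in order to build markers, so 51% or 88% is not the power of any test the plan specifies. The figures show relative precision only.
- Independence is optimistic. Allowing for clustering lowers every figure and narrows the gap at 1:4 from 12 points to about 8 or 9. The shortage of events dominates.
- 51 is not a ceiling. The Screening and recruitment strategy keeps recruitment open beyond 150 until the window closes, partly in case NEHAs are fewer than expected.

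The other PA analyses soften the point less. As noted above, neither compares pre-event change with event-free times, so the case-control step remains the main support for Objective 4. None of these points supplies a reason to sample.

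**Conclusion.** The point holds as a cheap improvement. With daily PA already in hand, sampling event-free times can equal but never better an analysis on all at-risk participant-days. In the illustration the cost runs from about 37 points of power at 1:1 to 12 at 1:4, 5 at 1:10 and 2 at 1:20. That rests on 51 independent events, 18.5% exposure, RR 2.5 and ratios that are assumed.

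A second tempting inference is that using all the time would secure 88% power. It would not. It adds no events; clustering in about 30 patients would lower the figure, and the Schoenfeld formula gives 72% even before clustering.

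**What to change.** Amend the PA and major health events section so that the pre-NEHA comparison and the PA-marker evaluation use all eligible at-risk participant-days. A suitable analysis is a discrete-time or recurrent-event model with PA change as a time-varying covariate, and a participant random effect or cluster-robust standard errors so that repeat episodes are handled. A sampled set can still be used for plots.

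If the sponsor prefers to keep a sampled comparison, state the ratio in advance (at least 20 control times per case) and account for clustering by participant.

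The cost is revised analysis wording and a little more analysis work, including a definition of which days count as at risk. No new data are needed.
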